Previous studies indicate that stroke patients may differentially respond to non-invasive motor cortex stimulation protocols according to whether the lesion includes cortex, or is confined to white matter (52). Accordingly, we will use blocked stratified randomization to ensure our two comparison groups are balanced with respect to this known prognostic factor (cortical versus subcortical classification). Classification of this grouping will be assessed using CT or MRI with 'subcortical' defined as a stroke without involvement of cortical motor areas, and 'cortical' as infarction of cortical primary or secondary sensorimotor areas in addition to subcortical infarction.

Randomization of patients is performed by a statistician and epidemiologist, [name]. She will communicate the status to [name]. The switch is covered so that the therapist and the PI will not know the group assignment.

Blinding

The study is double-blind. All investigators interacting with patients will be unaware which patients are receiving real or sham stimulation. This includes the principal investigator and research fellows conducting robotic, neurophysiology or clinical assessments. The tDCS device has a coding option to program sham or real stimulation. [name], a histopathologist in [name] lab who is not involved with the robot project and has agreed to perform this toggling task will set the tDCS device for any particular patient. She knows [name] and we will establish communication between [name] – who will determine the randomization and [name] so that [name] and the Research Associate to be named will not have the patient's code. It is important to note that once the machine to deliver the transcranial direct current stimulation is toggled no further manipulation of the device is needed. The tDCSM operates automatically to deliver current or not. We will receive the coding option from the collaborating institution, and will reveal this information after analysis, unless there is a need to inform the PI in case of an adverse event. Patients will be asked at visit 9 and visit 15 (mid-point and end of the intervention period), whether they think they received real or sham stimulation.

Statistical Considerations and Data Analysis

Specific Aim 1 (Clinical): Determine if there is a statistically significant difference in the change in upper limb Fugl-Meyer and Wolf Motor Function score between subjects trained with and without tDCS prior to robotic training.

Methods to address specific aim 1: We will compare demographic, clinical, kinematic, and tDCS variables between intervention groups using t-tests to compare means and chi-squared tests to compare proportions; where continuous data is non-parametric as defined by Shapiro-Wilk or Q-Q plots, we will use Kruskal Wallis tests. To assess the univariate relationship between treatment group and upper limb Fugl-Meyer score, repeated measures ANOVA will be used in order to account for longitudinal evaluations. Multivariate methods will include linear mixed models and ANCOVA to adjust for interactions or other covariates potentially contributing to the association between treatment and outcome. Further, Pearson correlation coefficients will be assessed to identify any linear association between kinematic, clinical and tDCS data points. The Spearman Rank correlation coefficient will be used for non-normally distributed variables. Like the Fugl-Meyer, secondary outcome measures, Wolf Motor Function, Barthel Index and Stroke Impact Scale are scored on a continuous scale and thus, will be analyzed as above. The MRC is scored on a scale from 0-5; Fisher analyses will be used to look for differences in strength between groups.

Specific Aim 2 (Kinematic): Determine if there is a statistically significant difference in a) mean speed, b) peak speed, c) smoothness, d) aim, and e) deviation from the straight line between subjects trained with and without tDCS prior to robotic training. This will be determined for both the trained tasks, as well as for the untrained, circle-drawing task. We will also include a static and dynamic quantitative measure of strength using the robotic device.

Methods to address specific aim 2: To assess the univariate relationship between treatment group and outcome, repeated measures ANOVA will be used in order to account for longitudinal evaluations. Multivariate methods will include linear mixed models and ANCOVA to adjust for interactions or other covariates potentially contributing to the association between treatment and outcome.

Specific Aim 3 (Neurophysiology): Determine if there is a statistically significant difference in: a) RMT, (b) MEP amplitude at 120% RMT, and c) SICI between subjects trained with and without tDCS prior to robotic training, both immediately following the training regimen, and 6 months later.

Methods to address specific aim 3: To assess the univariate relationship between treatment group and outcome, repeated measures ANOVA will be used in order to account for longitudinal evaluations. Multivariate methods will include linear mixed models and ANCOVA to adjust for interactions or other covariates potentially contributing to the association between treatment and outcome.

POWER: Based on the previous study by Lo et al., we can expect twelve weeks of upper limb robotic training to result in a 2.88 change in the FM score (5). We estimated that tDCS plus robotics would result in a FM change score of 4.33. Using a two-sided alpha and a standard deviation of approximately 1.5, enrolling 56 subjects (28 per group) would give us 90% power to detect a difference in Fugl-Myer score of 1.45 between the intervention groups. To account for potential subject attrition, we aim to increase our sample size by 15% thus resulting in an enrollment goal to 66 (33 subjects per group).

Specific Aim 4 (Clinical): Determine if there is a statistically significant difference in the change in verbal expression scores on the Apraxia Battery for Adults (ABA-2) and Philadelphia Naming Test Short Form (PNT short form) between subjects with aphasia trained with and without tDCS prior to robotic training.

Methods to address specific aim 4: We will compare demographic, clinical, and tDCS variables between intervention groups with aphasia using t-tests to compare means and chi-squared tests to compare proportions; where continuous data is non-parametric as defined by Shapiro-Wilk or Q-Q plots, we will use Kruskal Wallis tests. To assess the univariate relationship between treatment group and ABA-2 score, repeated measures ANOVA will be used in order to account for longitudinal evaluations. Multivariate methods will include linear mixed models and ANCOVA to adjust for interactions or other covariates potentially contributing to the association between treatment and outcome. Further, Pearson correlation coefficients will be assessed to identify any linear association between clinical and tDCS data points. The Spearman Rank correlation coefficient will be used for non-normally distributed variables. Fisher analyses will be used to look for differences in strength between groups.

Specific Aim 5 (Biological): Examine whether blood levels of HMGB-1, and TNF,IL-1, IL-6, IL-8, IL-10, and BDNF change across rehabilitation intervention, and if those changes are correlated to functional recovery.

Methods to address specific aim 5. **The statistical analysis for this pilot study will be primarily descriptive in nature. The main statistical analysis will employ repeated measures analysis to describe the patterns of change in HMGB-1 and the cytokine values over time. Other techniques will be explored if the data warrant it; such as examining**

pairs of outcome variables (HMGB-1 and TNF, HMGB-1 and IL-1, or HMGB-1 and stroke severity; as pioneered at Feinstein by [name] and as in [57]).

Protection of Human Subjects

RISKS TO SUBJECTS

Human Subject Involvement and Characteristics: We anticipate enrolling 66 human subjects. Inclusion and exclusion criteria are stated above in the Research Design and Methods section. Subjects will be enrolled into one of two sites: the Feinstein Institute for Medical Research or the Burke Medical Research Institute.

Sources of Material: Sources of research material for participants from Feinstein will be the hospital records providing demographic and medical information including CT or MRI imaging studies, and clinical examinations performed at outpatient facilities run by the Department of Physical Medicine and Rehabilitation of the North Shore University Hospital (NSUH) and LIJ Medical Center (LIJMC). Sources of research material for study participants at Burke Medical Research Institute will be obtained through hospital records at the Burke Rehabilitation Hospital in White Plains, NY, and overseen by the Burke IRB.

Potential Risks:

TMS Risks: TMS is a technique that has been used widely and in a growing number of laboratories since 1985. A consensus was reached at the International Safety Conference on Transcranial Magnetic Stimulation, held at the National Institutes of Health in June of 1996, that single-pulse TMS and slow rTMS (with rates of stimulation less than one Hz) are safe. Subjects may experience mild headaches or neck pain, which are believed to be due to muscle tension and from the straight posture of the head and neck during the application of TMS. A rare possibility of activating a seizure in susceptible subjects has been documented.

tDCS Risks: tDCS is a safe technique that poses a non-significant risk to participants. The safety of this technique has been addressed and tested by multiple researchers (38, 40-42, 45, 46) who have concluded that tDCS, as applied in a manner similar to our proposed protocol has no long-term negative side effects. More than 30 research studies involving hundreds of participants have been published using tDCS. Hundreds more participants have undergone tDCS for unpublished pilot research (46). No undesirable or long-lasting effects have been reported, nor have any participants reportedly abandoned a study due to discomfort.

Researchers at the National Institute of Neurological Disorders and Stroke (NINDS) conducted a safety study on tDCS, investigating 20-minute sessions of 1 mA and 2 mA current stimulation with healthy controls (n=103) (45). No negative effects were identified. Nitsche and colleagues (2004) found no measurable structural changes in brain tissue due to tDCS (64). Additionally, studies have shown that tDCS can be used safely in stroke patients (38, 40, 41, 47). Thus, a growing body of research from different laboratories has shown that tDCS is a safe, non-invasive and painless technique for modulating neural excitability, with measurable but only transient effects. The protocol described here uses stimulation levels that fall well within safety limits established by basic research investigating neural tissue damage, as well as numerous studies applying tDCS with human participants (64-66). tDCS has the potential to cause erythema – redness of the skin that is uniform or mottled around the area of stimulation. The reddening has been found to be transient for levels of stimulation proposed in this protocol (45). 2005).

Nitsche and colleagues (2003) reported that, in unpublished research, stimulation at electrical current levels above 1 mA can be uncomfortable for subjects. No such discomfort was reported in the NINDS safety study conducted by Iyer and colleagues (2005), in which 103 participants were stimulated at levels higher than those used by Nitsche and colleagues (2003).

Robot Risks: There are no known risks associated with the use of robotic training for stroke rehabilitation. Some patients have pain in the shoulder after a stroke. Our experience has demonstrated a comparable incidence of shoulder pain in groups that were or were not treated by the robot.

Blood Draw Risk: Minimal risks of blood withdrawal include pain from the needle being inserted through the skin into the vein, bruising, clot formation under the skin, lightheadedness, possible fainting and rarely infection.

Confidentiality Risk: One additional risk concerns the risk to confidentiality incurred with any collection of medical data.

ADEQUACY OF PROTECTION AGAINST RISKS

Recruitment and Informed Consent: Stroke subjects who meet inclusion criteria and do not meet exclusion criteria will be recruited at two sites by consenting professionals: the Burke Rehabilitation Hospital and the Department of Physical Medicine and Rehabilitation of NSUH and LIJMC.. Recruitment will be done with direct contact, flyers and letters sent to patients who have been enrolled on other research projects.

Recruitment of patients at Burke Rehabilitation Hospital will be primarily based on screening of the Burke outpatient list, as well as inpatient medical records for identifying future candidates, physician referral, advertising within the Burke network, on the Burke Website and collaborator websites. Participants enrolled at the Burke Medical Research Institute study site will be overseen by the Burke IRB, and its associated, approved study protocol and consent form.

Northwell Health physicians who have appropriate patient populations will be made aware of the research study protocol and procedures, and given an overview of the study through contacts with the study personnel. The physician will identify potential study participants. If the patient expresses interest in participation, the physician will either 1) obtain informed consent (if they are listed as an investigator on this study) or 2) provide the patient with the study coordinator's contact information or 3) provide the patient's contact information to study personnel with the patient's permission, which will be documented in the medical record.

After a discussion about the study with a potential subject and a potential subject's legally authorized representative (LAR)/next of kin, interested parties will be given a copy of the consent form by one of the study investigators. The investigator will review and explain the consent form. All information about the study will be provided. Ample time will be given for individuals to ask questions regarding participation and to have questions answered prior to signing the consent form. If so desired, those interested will be given a copy of the consent form so that they may have the opportunity to discuss participation further with family and/or advisors. Only those investigators listed in the study protocol will obtain informed consent. If an individual chooses to enroll, the consent form will be signed before participation begins. Once an individual joins the study and informed consent is obtained, the subject will receive a signed

copy of the consent form. The subject may withdraw from the study at any time without repercussions to subsequent care.

If the patient is awake, alert, and oriented to person, place, and time, and demonstrates appropriate cognitive and communicative abilities as determined by the treating physician, the patient will be deemed to have the appropriate capacity to consent; however, given that borderline cognitive dysfunction and/or aphasia may not be easily distinguishable, the patient's LAR/next of kin will be routinely included when consent to participate is being obtained for all subjects.

If it is determined that a patient is unable to consent for him/herself, due to a lack of capacity or lack of comprehension, consent will be sought from the patient's LAR/next of kin. Assent of the adult subject with LAR/next-of-kin will be obtained as appropriate. If such a subject regains his/her ability to make healthcare decisions, he/she will be given the opportunity to provide consent. This consent will be documented using the Addendum to Consent by Research Proxy for Continuing Participation in a Research Study form.

If the patient provides the consent delegate with assent to participate in the research but, due to a physical disability, is unable to sign the consent form, the patient will provide verbal consent and a witness and the patient's LAR/next of kin will sign the document affirming their presence during the consent process and the patient's physical disability as reason for an absent signature.

A study investigator will obtain informed consent, in person, from interested persons. After a discussion about the study with a potential subject, interested persons will be given a copy of the consent form by one of the study investigators. The investigator will review and explain the consent form to the person. All information about the study will be provided. Ample time will be given for persons to ask questions regarding participation and to have questions answered prior to signing the consent form. If so desired, those interested will be given a copy of the consent form so that they may have the opportunity to discuss participation further with family and/or advisors.

Investigators may contact (or be contacted by) a potential subject's LAR/next-of-kin by telephone to discuss participation in this research protocol. The investigator will provide subject's LAR/next-of-kin with all the information contained in the written consent form. The investigator will answer any questions regarding the research and give the subject's LAR/next-of-kin ample time to consider participation in the study which may require a follow-up phone conversation.

If the subject's LAR/next-of-kin agrees to allow the decisionally incapacitated patient to participate in the research study, the investigator will provide his/her contact information. The investigator will explain (and repeat) the next steps necessary for the LAR/next-of-kin to provide informed consent, which include the following processes. A written consent form will be sent to the LAR/next-of-kin as an email attachment, or left at the nurses' station on the unit where the potential subject is an inpatient. The LAR/next-of-kin must read the consent form and call or email the investigator if he/she to discuss research and resolve issues/questions. If subject's LAR/next-of-kin agrees to participation in the protocol, the investigator will direct him/her to sign the consent form and return it to the investigator by mail or fax. Another option would be to scan the signed consent form to a PDF file and return it to the investigator as an email attachment. An enrollment note must be written by the investigator documenting all phone conversations with the LAR/next-of-kin. Printouts of any email correspondence must be placed in the subject's

research chart. After the signed consent form is received, investigator will sign the consent form. A copy will be made and sent to the LAR/next-of-kin for his/her records. In cases where consent is obtained by e-mail/mail, investigators request a waiver for the need for a witness signature.

In the event that a subject and/or LAR/next of kin arrives for the first evaluation and then requests to take the consent form home for review prior to signing it, minimal risk clinical measures of the subject's upper extremity function may still be collected during the initial study visit, prior to the signing of the consent, in order to reduce the burden on the disabled subject and their family who would otherwise be required to come for an additional study visit. If that subject and/or their LAR/next of kin then decline further participation in the study, the data for that subject's first evaluation will be destroyed.

Only those investigators listed in the study protocol will obtain informed consent. If a person chooses to enroll, the consent form will be signed before participation begins. Once an individual joins the study and informed consent is obtained, the subject will receive a signed copy of the consent form. The subject may withdraw from the study at any time without repercussions to subsequent care.

Protection Against Risk:

Protection against TMS-related risk: All participants will be screened twice for seizure-related risk factors (visit 1 & visit 4). Seizure-susceptible patients will be excluded from the study by using this screening questionnaire. sEMG has no known risks. We will monitor subjects continually during the stimulation period, and will be in constant contact with the subjects. The study can be immediately stopped at the subject's request.

Protection against tDCS-related risks: If any redness is apparent where the electrodes were placed, a cold compress will be offered to the subject. We will monitor subjects continually during the stimulation period, and will be in constant contact with the subjects. The study can be immediately stopped at the subject's request.

Protection against Robot-related risk: The practical issues regarding the robot control system and patient safety include that the software that runs the robot device continuously checks the force, speed and position of the robot arm and on the status of the power. This software can brake the robot if the force, speed, or position is beyond set ranges. There are two clearly visible "shut-down" switches that are always in reach of the technician trainer. In the event of software failure, motion beyond the specified range, loss of electrical power, or activation of the "shut-down" switch the device stops (brakes) within 2 milliseconds. The robotic arm will only move the patient's upper limb, and no other body part will be within the active range of this movement (the head for example is well out of the possible range of the movement of the robotic arm). The patient's hand is attached to the robotic arm with a magnetic clasp, which can be released with a sudden pull from the patient or therapist. The entire apparatus is ground-fault protected to exceed clinical standards. We will monitor subjects continually during robotic training, and will be in constant contact with the subjects. The study can be immediately stopped at the subject's request.

Protection of Confidentiality: To protect subjects' confidentiality, each subject will be assigned a number, and all data will be stored with the subject number only and not the subject's name. Data will be stored on a password-protected computer and on the cloud data server, REDcap, which is encrypted and password protected. Subject charts with medical history and assigned subject numbers will be kept in locked file cabinets stored at either the Feinstein robot suite for patients enrolled through Northwell Health or the Burke robot suite for patients enrolled through

Burke Rehabilitation Hospital. Access to charts will be granted only to study investigators at Feinstein and Burke, and CRC staff. Charts will be kept confidential and will not be shared with any third parties without permission from the subject. Any study data containing PHI that is transferred between investigators at Feinstein and collaborating institutes will be shared via encrypted email or encrypted storage drives.

Of note, [name] is a sub-investigator from MIT and will be assisting in the analysis of data only. Subject data they receive from this research study will be de-identified.

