Inclusion/Exclusion Criteria

Inclusion Criteria:

1. ≥ 18 years of age
2. First single focal unilateral lesion with diagnosis verified by brain imaging (MRI or CT scans) that occurred at least 6 months prior;
3. Cognitive function sufficient to understand the experiments and follow instructions (Mini-Mental Status Score of 24 or higher or interview for aphasic subjects);
4. Fugl-Meyer assessment 7 to 58 out of 66 (neither hemiplegic nor fully recovered motor function in the muscles of the shoulder and elbow and wrist).

Exclusion Criteria:

1. Botox treatment within 6-weeks of enrollment;
2. Fixed contraction deformity in the affected limb;
3. Complete and total flaccid paralysis of all shoulder and elbow motor performance;
4. History of hemorrhagic stroke
5. Ongoing use of CNS-active medications
6. Ongoing use of psychoactive medications, such as stimulants, antidepressants, and anti-psychotic medications
7. Presence of additional potential tDCS / TMS risk factors:
 - Damaged skin at the site of stimulation (i.e., skin with ingrown hairs, acne, razor nicks, wounds that have not healed, recent scar tissue, broken skin, etc.)
 - Presence of an electrically, magnetically or mechanically activated implant (including cardiac pacemaker), an intracerebral vascular clip, or any other electrically sensitive support system

- Metal in any part of the body, including metal injury to the eye (jewelry must be removed during stimulation)
- A history of medication-resistant epilepsy in the family
- Past history of seizures or unexplained spells of loss of consciousness

Visit Schedule

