Verbal production of Action vs. Nonaction words: Network models of language suppose that motor acts and the words used to describe them are a part of the same neural network. tDCS stimulation of the motor cortex may produce enhanced verbal production of action vs. nonaction words (69, 70).

Connected Speech Sample including the “Cookie Theft” or “Birthday Party” picture descriptions: Connected speech samples are frequently used metrics of changes in rate, fluency, and language formulation in individuals with aphasia. Audio/visual recordings of naturalistic language samples allow for independent quantitative scoring of language function by clinicians (78, 79).

“Repetition” subtest of the Aphasia Diagnostic Profile (ADP): The ADP is a valid and reliable measure of changes in repetition and verbal facility for simple sentences and basic reflexive speech (78, 79).

“Symbol Cancellation” subtest of the Cognitive Linguistic Quick Test (CLQT): is a valid and reliable non-verbal, visual cancellation task. It is frequently used by clinicians in aphasia literature as a non-verbal control task of attention and visual memory (76).

Western Aphasia Battery Revised (WAB-R): The WAB-R provides an aphasia quotient for type and severity of aphasia, and is commonly used in the aphasia literature. Changes of >5 points are clinically significant (75, 77, 78).

TMS Evaluation

Screening: A questionnaire to screen for TMS risk factors, published for use with TMS research, will be completed by every participant prior to undergoing TMS (67). An answer of “yes” to any of the listed questions will necessitate further inquiry by the investigator, but not necessarily exclusion from the TMS study.

Motor cortex stimulation and electromyography: Patients will sit comfortably in a chair and the investigator will gently apply the TMS wand against the skull. There will be a clicking noise that indicates the stimulator is generating a magnetic field and the sound will be followed by a muscle twitch in the opposite arm, forearm or hand.

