We will use Brainsight™ neuronavigation to deliver stimuli on a grid in 1-cm steps in the coronal and sagittal planes, over the region of the primary motor cortex in the affected hemisphere. TMS will be delivered using a MagPro X100 stimulator with a 5 cm diameter figure-of-eight coil, held tangential to the skull and aligned in the para-sagittal plane with the handle rotated 45° lateral. Surface electromyographic (sEMG) recordings will be made from electrodes positioned over the muscle belly of the right flexor carpi radialis (FCR) muscle. EMG signals will be amplified (x1000) and band-pass filtered between 20 and 1000 Hz, before being digitized at 2000 Hz for 100 ms following each stimulation, using a Cambridge Electronic Design (CED) acquisition system. The optimal site of stimulation for FCR will be determined from initial exploration, and used throughout the experiment.

Resting Motor Threshold (RMT): Motor evoked potentials (MEP) recorded via surface EMG during the torque recordings, will be analyzed for peak-to-peak amplitude. The lowest stimulus intensity evoking a MEP of 50 μ V in at least five of ten trials in the relaxed muscle will be used. We will use 2% increments in stimulator output starting just below the intensity determined from initial exploration. Motor threshold is considered to reflect membrane-related intrinsic neuronal excitability. Ten MEP responses with single stimuli delivered at 120% RMT intensity will be recorded, to determine if a change in amplitude is observed at each time point.

Intracortical Inhibition: A single pulse TMS stimulus can be inhibited or facilitated if preceded by a subthreshold conditioning stimulus (Short Interval Cortical Inhibition SICI, 3msec inter-stimulus interval) is an accepted measure to determine if changes in corticospinal output are related to altered intracortical excitability. We will record 10 test MEPs, and 10 conditioned MEPs (80%RMT conditioning TMS intensity, test intensity adjusted to give 1mV amplitude MEPs) for SICI. Conditioned and unconditioned pulses will be randomly presented.

The frequency of TMS stimulation will not exceed 0.2 Hz, as this will avoid cumulative effects of the stimulation during assessment.

Transcranial Direct Current Stimulation (tDCS) Application

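### EMG is fixed on the right forearm while TMS targets the affected hemisphere, so as written the Aim 3 measures cannot be validly obtained in left-hemiparetic patients

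*Combined protocol and SAP*

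**What the plan says.** Under TMS Evaluation, the paragraphs on motor cortex stimulation and electromyography apply stimuli on a grid "over the region of the primary motor cortex in the affected hemisphere". The same text describes the expected response: "the sound will be followed by a muscle twitch in the opposite arm, forearm or hand". The recording is made with "electrodes positioned over the muscle belly of the right flexor carpi radialis (FCR) muscle". No exception is given for patients whose paretic arm is the left.

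The later steps build on that recording:

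- **Stimulation site:** "The optimal site of stimulation for FCR will be determined from initial exploration", and that site is kept for the rest of the experiment.
- **Resting motor threshold (RMT):** the lowest intensity giving a 50 microvolt MEP "in at least five of ten trials in the relaxed muscle will be used". Ten further responses are then taken at 120% of RMT.
- **SICI:** the conditioning pulse is set at 80% of RMT, with "test intensity adjusted to give 1mV amplitude MEPs".

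The Specific Aim 3 paragraph of Statistical Considerations and Data Analysis names the endpoints to be compared: "a) RMT, (b) MEP amplitude at 120% RMT, and c) SICI between subjects trained with and without tDCS".

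On side of lesion, the inclusion criteria require only a "First single focal unilateral lesion with diagnosis verified by brain imaging". Neither hemisphere is specified. In the six-patient pilot under Preliminary Data, two had right and four had left hemiparesis.

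**The concern.** The stimulated side follows the patient's lesion, whereas the recorded side is fixed. The two agree only when the lesion is in the left hemisphere. For a lesion on the right, the plan stimulates one motor pathway and records from a muscle that pathway is not expected to drive.

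At stake is Aim 3, the mechanistic aim, in an eligible subgroup that could be about half the trial. Staff who followed the text would find no adequate response, or would record a signal that does not describe the treated pathway. Staff who noticed would have to depart from the written procedure, at two sites, with nothing in the plan telling them how. The TMS section and the Aim 3 methods give no rule for a patient without an MEP. Because eligibility extends down to a Fugl-Meyer score of 7, an absent response could also be put down to stroke severity rather than to a misplaced electrode. That last point is an inference, not something the documents state.

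**Working it through.** The plan gives no sample size or power for Aim 3, so there is no stated figure to reproduce. The check is mainly one of side against side.

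**Step 1. Which muscle is recorded, by side of paresis**

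| | Right hemiparesis | Left hemiparesis |
|---|---|---|
| Affected hemisphere (coil) | Left | Right |
| Arm expected to respond (opposite) | Right | Left |
| Arm with the electrode (as written) | Right | Right |
| Recorded muscle | Affected limb, opposite the coil | Unaffected limb, same side as the coil |
| Expected MEP captured? | Yes | No |

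**Step 2. What depends on the MEP**

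- The optimal site for the flexor carpi radialis (FCR) is found from responses in that muscle.
- RMT is defined by 50 microvolt responses in five of ten trials.
- The amplitude endpoint is taken at 120% of RMT, so it needs both RMT and an MEP.
- SICI needs a 1 mV test response and a conditioning pulse at 80% of RMT.

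All three endpoints therefore fail together for the treated pathway when the recorded muscle is on the wrong side.

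**Step 3. Whether other text corrects the side**

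- *tDCS Application* refers to the affected limb and to the FCR site found by TMS. That text governs where the anode goes, not where the EMG is recorded.
- *Specific Aim 3* mentions wrist and elbow muscles and gives no side.

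Both suggest that the affected limb was meant. Neither replaces the instruction.

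**Step 4. How many patients the instruction is wrong for**

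The share *p* with left hemiparesis is not stated. Assume *p* between 0.40 and 0.60.

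- Whole trial: 0.40 × 66 = 26.4 and 0.60 × 66 = 39.6, so about 26–40 of 66.
- Per arm, in expectation: 0.40 × 33 = 13.2 and 0.60 × 33 = 19.8, so about 13–20 of 33.
- Pilot share: 4/6 = 0.67, with an exact (Clopper-Pearson) 95% interval of 0.223–0.957. This is too wide to narrow the assumed range.

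**Step 5. Illustrative worst case**

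Suppose every recording from left-hemiparetic patients were lost and everyone else gave usable data. With *n* evaluable patients per arm, the standardised difference detectable with 80% power at two-sided 0.05, without attrition, is (1.960 + 0.842) × √(2/*n*).

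| Share with left hemiparesis | *n* per arm | Detectable difference (SD) |
|---|---|---|
| None lost | 33 | 0.69 |
| 40% | 33 × 0.60 = 19.8 | 0.89 |
| 50% | 33 × 0.50 = 16.5 | 0.98 |
| 60% | 33 × 0.40 = 13.2 | 1.09 |

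These values show only how far Aim 3 could be weakened if nobody corrected the electrode position.

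**The case against.** The strongest reply is that this is a one-word slip whose intended meaning is clear. The tDCS Application section describes the anode position in two ways: as the point where TMS gives the strongest contraction of the affected limb, and as the FCR site found by TMS. The two can be the same place only if the FCR in question belongs to the affected limb. Because the anode cannot be placed without that site, staff must look for an affected-limb response in every patient. A right-arm electrode on a left-hemiparetic patient would conflict with that step at once and could simply be moved. On this view the matter is minor wording, the patient counts only say for whom a word is wrong, and the worst-case figures assume an error that nobody notices.

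Much of this stands. The word is probably a carry-over, the error would likely be seen at set-up, and neither the counts nor the detectable differences predict data loss. It does not remove the point. The recording paragraph is the operative procedure that defines three endpoints, and no other text overrides it. Noticing the problem leads to an unwritten departure from procedure, possibly handled differently at the two sites.

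It is also fair to say that the Aims describe EMG from wrist and elbow flexors and extensors, while the recording paragraph names the FCR alone. Correcting the side does not resolve that separate mismatch.

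**Conclusion.** The concern holds as written. In patients with left hemiparesis, the stated electrode position records the unaffected arm, and RMT, MEP amplitude and SICI cannot be validly obtained for the treated pathway. The instruction is wrong for about 26–40 of 66 patients if 40–60% have left hemiparesis, a share that is assumed.

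The realistic consequence is lost or delayed recordings, or improvised corrections, rather than failure of the whole aim. No bias between arms is shown: side of paresis is balanced in expectation by randomisation, although the Randomization section stratifies only by cortical versus subcortical lesion. The Fugl-Meyer outcome does not use EMG, and the anode site remains defined by contraction in the affected limb. The error should be fixed because it misdirects the measurement of a whole aim in an eligible subgroup, but it does not threaten the primary result.

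**What to change.** In the electromyography paragraph of TMS Evaluation, replace *right flexor carpi radialis* with *flexor carpi radialis of the affected limb*. This brings the recording side into line with the stimulated hemisphere and with the affected-limb wording used for anode placement. In principle, all 66 enrolled patients then become measurable for Aim 3.

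The cost is one phrase. No procedure, visit or patient is added, and no figure in the plan changes.
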